##### **4.8.2 Treatment Visits – Visits 1-24 (Weeks 1-12)**

The Treatment Sessions will occur twice weekly for twelve weeks at MGH Depression Clinical and Research Program (DCRP) in Boston and at NYUSOM Nathan S. Kline Institute (NKI), Orangeburg, NY. Subjects missing one session will be allowed to still receive their treatment within the same week. The study PI will be an active participant in the delivery of the TLT. The PI and other collaborators from MGH DCRP and at NYUSOM NKI will assist with the delivery of TLT. The device (TPBM-1000) for the

administration of the TLT will be provided by Litecure Inc. Litecure will provide training of MGH DCRP and NYUSOM NKI staff in the use of the device and will provide training certificates at the completion of the training.

The overall session is estimated to last about 25 min. Study sessions will take place in an office dedicated to TLT treatment at MGH DCRP and at NYUSOM NKI. Only the subject and the staff administering the TLT will be allowed during the session. The subject will comfortably lie down on an exam bed or sit on recliner. The sites of application of TLT (left and right forehead) will be inspected for any possible skin lesions (e.g. laceration or signs of inflammation) which would contraindicate the treatment. During treatment sessions the office will be kept completely dark and a warning sign will be hanged at the office door. The staff will be provided training on basic safety procedures relative to the use of the device.

The trained staff administering the TLT will use utmost care to never shine the light in or near the eyes of the subject safety goggles will be selected based on the TLT biophysical properties, in accordance to the Occupational Safety and Health Administration (OSHA) guidelines. The delivery of the TLT is expected to last 20 min total (simultaneous application on the left and right forehead). The subject will be asked to rest for five minutes after the delivery of TLT. The skin at the sites of the application will be inspected again prior to dismissing the subject. A log with the dates of treatment delivery per each study subject will be kept at MGH DCRP (Boston) and at NYUSOM NKI, NY.

#### ***4.8.2.1 Treatment Visit 1***

During Treatment Visit 1, subjects will be randomized to either TLT or Sham. The following will be performed prior to treatment and serve as baseline values:

- HAM-D-17
- QIDS-C
- CGI
- C-SSRS
- ADVERSE EVENTS FORM
- CADSS
- Concomitant medications form
- ASQ (self-rated)
- SAFTEE-SI (self-rated)
- SDQ (self-rated)
- NEURO-QOL (self-rated)
- SFI (self-rated)
- PEG (self-rated)
- Cognitive tests

#### **4.8.2.2 Screening Visit, Visit 13, and Visit 25**

During these visits, approximately 2-6 cc of blood will be drawn to conduct cytokine assays.

Patients shall be instructed to contact the investigator or a member of his staff at any time between visits concerning adverse events or worsening of symptoms.

#### **4.8.2.3 Treatment Visits 2-24**

During Treatment Visits 2-24, subjects will undergo a treatment procedure. At Visit 7, 13 and 19 the HAMD17 scale will be administered. At Visit 10 and 22 only, subjects will undergo a TSRQ assessment post-treatment. At visits 10 and 22, subjects and raters will complete the Perception of Blindness Questionnaire. The PEG (self-rated) will be administered at visit 13.

Cognitive testing will be computerized and performed at Visits 7, 13 and 19. Weight and vitals will be recorded at visit 13. The CADSS will be administered at visit 13. During visit 10 and visit 22 the PBQ will administered. In addition to treatment, at Visits 3, 5, 7, 9, 11, 13, 15, 17, 19, 21 and 23, the following will be performed prior to treatment:

- QIDS-C
- CGI
- C-SSRS
- ADVERSE EVENTS FORM
- Concomitant medications form
- ASQ (self-rated)
- SAFTEE-SI (self-rated)
- SDQ (self-rated)
- NEURO-QOL (self-rated)
- SFI (self-rated),

Patients will be instructed to contact the investigator or a member of his staff at any time between visits concerning adverse events or worsening of symptoms.

#### **4.8.3 Post-Treatment Visit – Visit 25, (Week 13)**

After treatment completion, subjects will continue with one more clinical study visit to measure the long-term antidepressant effect of TLT. Post TLT administration, subjects will be permitted to start or change treatment with antidepressant medications, as clinically necessary (and at any time in the study if severe worsening of depressive symptoms – see 4.8.4 Termination). Cognitive testing will be performed.

At Visit 25, the following will be performed:

- Vital Signs and weight
- HAM-D-17

- QIDS-C
- CGI
- C-SSRS
- CADSS
- ADVERSE EVENTS FORM
- Concomitant medications form
- ASQ (self-rated)
- SAFTEE-SI (self-rated)
- SDQ (self-rated)
- NEURO-QOL (self-rated)
- SFI (self-rated)
- PEG (self-rated)

#### 4.8.4 Termination

We will encourage subjects to continue enrollment in the study via follow-up visits regardless of discontinuation of the TLT/ sham. At the end of the study, we will refer the subjects to their counselor and /or psychiatrist. If the CGI-S increases more than 2 points during the study, the subject will be counseled to start or change to an FDA-approved antidepressant medication. If the CGI-S increases above score-5 or if a subject becomes actively suicidal based on the C-SSRS scale, the subject will be counseled to start (or switch if already on) an FDA-approved antidepressant medication. Subjects who are deemed actively suicidal and are in imminent danger will be escorted to the local psychiatric Emergency Department at MGH or NYUSOM for evaluation and subsequent hospitalization; they will also be terminated from the study. If the subject is appropriate for outpatient monitoring, the subject will be followed with frequent appointments outside the study. Each subject will have the Investigator's contact information as well as instructions on how to call for emergency services, if needed.

#### 4.9 Scales & Forms

We will offer clinical interviews and study forms in English. All scales will explore the past 7 days except for M.I.N.I (life-time), TSRQ (study duration).

- **(M.I.N.I)** – The M.I.N.I. is a short structured diagnostic interview, developed jointly by psychiatrists and clinicians in the United States and Europe, for DSM and ICD psychiatric disorders. With an administration time of approximately 15 minutes, it is designed to meet the need for a short but accurate structured psychiatric interview for clinical trials. According to researchers at the National Institute of Mental Health's (NIMH) Division of Clinical and Treatment Research, the M.I.N.I. is a fully validated and more time-efficient alternative to the Structured Clinical Interview for DSM Disorders (SCID) (Sheehan et al., 1998)
- **Quick Inventory of Depressive Symptomatology- Clinician Rated Scale (QIDS-C)** – This is a brief (16-item) clinician-rated inventory of core depressive symptoms such as sleep, depressed mood, appetite, concentration, suicidal ideation, interest, energy, psychomotor retardation or agitation.

- **Hamilton Depression Rating Scale – 17 items (HAM-D-17; Hamilton, 1960)** – This instrument is completed by the clinician based on his/her assessment of the patient's depressive symptoms, using a structured interview and defined anchor points. The HAM-D aims to quantify the degree of depression in patients who already have a diagnosis of major depression. Questions focus on neurovegetative and other depressive symptoms experienced over the past 7 days. Several different versions of the HAM-D exist; they differ only in the number of questions included. The standard form which is generally used in research studies is the 17-item Hamilton D (HAM-D-17). Answers to questions are rated on a scale of 0-4 or 0-2, with higher scores indicating more severe pathology. Scores on the HAM-D-17 typically fall into the following ranges: a) not depressed = 0-7; b) mildly depressed = 8-13; c) moderately depressed = 14-18; d) severely depressed = 19-22; e) very severely depressed = 23 and over.
- **Symptoms of Depression Questionnaire (SDQ)** – This is a comprehensive measure of depression that includes the assessment of symptoms in the anxiety–depression spectrum. It assesses irritability, anger attacks, and anxiety symptoms together with the commonly considered symptoms of depression. Analysis of the factor structure of the SDQ identified 5 subscales, including one in the anxiety–depression spectrum, with adequate internal consistency and concurrent validity (Pedrelli et al., 2014).
- **Anxiety Symptoms Questionnaire (ASQ)** – This, is a 17-item self-report questionnaire measuring the frequency and intensity of 17 symptoms of anxiety, including nervousness, worrying, irritability, trouble relaxing, insomnia, lack of energy, difficulty concentrating, somatic symptoms, and impairment in functioning due to anxiety.
- **Clinical Global Impressions – Severity and Improvement (CGI-S, CGI-I)** – These two instruments are scored 1-7 by the clinician based on assessment of the subject's overall clinical status. They measure, based on history and scores on other instruments: (a) depressive severity (CGI-S) and (b) clinical improvement (CGI-I).
- **Columbia Suicide Severity Rating Scale (C-SSRS)** for suicidal ideation and behaviors: an instrument endorsed by the FDA for clinical trials. This instrument systematically tracks suicidal ideation and behavior (e.g., suicide attempts, wish to die, thoughts of suicide, plan and intent) (Posner et al. 2007).
- **Systematic Assessment for Treatment Emergent Events (SAFTEE-SI)** – The SAFTEE is a commonly used instrument originally developed by NIMH and adapted into a self-report instrument. The version of the scale that we plan to use is the same used by the multi-center, NIMH-sponsored CO-MED trial, and it examines in a systematic fashion all possible treatment-emergent side effects and probes specific adverse symptoms, including suicidal thoughts and behaviors, and self-injurious behavior.
- **Adverse Events Form-** the Adverse Events Form captures any adverse event (serious or otherwise) specifically related to the application of the TLT. This form will help to determine if the side effects of the TLT are too great for a participant to continue in the study.

- **Quality of Life in Neurological Disorders (Neuro-QoL Item Bank v2.0 – cognition function– short form)** - The cognitive section of the Neuro-QoL is an 8 item self-rated measure of both executive function and general concerns. It measures perceived difficulties in cognitive abilities (e.g., memory, attention, and decision making) or in the application of such abilities to everyday tasks (e.g., planning, organizing, calculating, remembering and learning).
- **Massachusetts General Hospital Sexual Functioning Inventory (MGH-SFI)** - This is a patient-rated self-report outcome measure that quantifies sexual dysfunction into 5 functional domains (“interest in sex,” “sexual arousal,” “ability to achieve orgasm,” “ability to maintain erection” [males only], and “sexual satisfaction”).
- **The TLT Self-Report Questionnaire (TSRQ)** – An open-ended questionnaire focusing on potential inconveniences and discomforts from the TLT. It will be offered after at least two TLT sessions have been delivered.
- **Concomitant medications form** – This form will be completed at every TLT study visit, including the screening visit, as a safety-monitoring tool.
- **Montreal Cognitive Assessment (MoCA)**: This is a 10-item rapid screening instrument for mild cognitive dysfunction. It assesses different cognitive domains: attention and concentration, executive functions, memory, language, visuoconstructional skills, conceptual thinking, calculations, and orientation. This measure will be used to assess entry criteria (Nasreddine et al. 2005).
- **The Clinician Administered Dissociative Symptoms Scale (CADSS)**: This is a 23-item clinician-administered scale for the assessment of dissociative symptoms. The CADSS can measure the amount of change in participants dissociations from the beginning of a study or treatment to the end. The CADSS consists of both subjective and objective questions. For a person in dissociation the experience is subjective, and although, dissociation is an individual’s cognitive process, dissociation is still observable by other. It will be measured for the “past 6 weeks” at baseline, and after 6 and 12 weeks into the study (Bremner, et al., 1998).
- **The Massachusetts General Hospital (MGH) Antidepressant Treatment Response Questionnaire (ATRQ)**: a scale used to determine treatment resistance in major depressive disorder (MDD). The ATRQ examines the efficacy (improvement from 0% [not improved at all] to 100% [completely improved]), and adequacy (adequate duration and dose) of any antidepressant treatment in a step-by-step procedure.
- **The Perceptions of Blinding Questionnaire (PBQ): The Perceptions of Blinding Questionnaire (PBQ)**: the PBQ is a self-report questionnaire to determine the degree to which the participant believes s/he is receiving the treatment or the sham.
- **PEG Assessment**: The PEG is a self-report questionnaire with three questions used to assess pain severity and interference with daily life.

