#### ***4.17 Clinical Adverse Events***

##### **4.17.1 Overview and Definitions**

All adverse events will be recorded from the time of Informed Consent through study completion, or termination. The Adverse Event CRF must be completed and submitted to the IRB, FDA, and Litecure, as required. Regulations for adverse event handling and reporting contained in the FDA and ICH Guidelines will be adhered to.

Consideration of Adverse Events will hereafter consist of Adverse Events, Serious Adverse Events, and Adverse Device Effects, including Anticipated Adverse Device Effects and Unanticipated Adverse Device Effects.

- Adverse Event is defined as any untoward/undesirable clinical occurrence in a clinical investigation of a subject using a device and/or product and which does not necessarily have a causal relationship with this treatment. An Adverse Event can therefore be any unfavorable and/or unintended sign, symptom, or disease temporally associated with the use of a device product, whether or not considered

related to the device product. Only abnormal laboratory values that are deemed clinically significant by the investigator will be classified as adverse events.

- Serious Adverse Event is defined as any untoward/undesirable adverse experience that results in any of the following outcomes: 1) death; 2) a life-threatening adverse experience; 3) inpatient hospitalization or prolongation of existing hospitalization; 4) a permanent/persistent or significant disability/incapacity or a congenital anomaly/birth defect; 5) important medical events that may not result in death, be life-threatening, or require hospitalization may be considered a serious adverse experience when, based upon appropriate medical judgment, they may jeopardize the subject and may require medical or surgical intervention to prevent one of the outcomes listed in this definition.
- Anticipated Adverse Device Effect is defined as any adverse effect related to the device or procedure, which is identified in the protocol.

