#### **4.17.3 Reporting Procedures for All Adverse Events**

After review with the subject by the study site personnel, all Adverse Events occurring during the study, whether or not attributed to the TPBM-1000 device or TLT procedure, observed by the Investigator or reported by the subject, will be documented in the subject's source document and on the appropriate CRF pages. The following attributes must be assigned:

1. Description of event
2. Date of onset
3. Date of resolution (if applicable)
4. Seriousness
5. Relationship to the study device and/or procedure(s)
6. Intensity

7. Action(s) taken
8. Outcome(s)

Intensity is defined as a measure of the severity of a reaction, effect or experience. The measurement(s) are described as mild, moderate or severe. The event itself, however, may be of relative minor medical significance.

The intensity of Adverse Events is assessed as mild, moderate or severe according to the following index scale:

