**None**

The Adverse Event is not associated with the study device use.

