### 5.2 Specific Aims

A. To assess the antidepressant effect of the Transcranial continuous or pulse Light Therapy in depressed subjects.

Hypothesis 1: We anticipate that TLT will decrease QIDS-C and HAM-D 17 total scores in study subjects significantly more than the Sham treatment. We expect that we will be also able to estimate the effect size of the antidepressant action of Transcranial continuous and pulse Light Therapy, separately.

B. To assess the safety and tolerability of the Transcranial continuous / pulse Therapy in depressed subjects

Hypothesis 2: We predict that the Transcranial continuous and pulse Light Therapy will be safe and well-tolerated by depressed patients, as assessed by the following rating scales: SAFTEE-SI and ADVERSE EVENTS FORM. We anticipate differences in between TLT and Sham treatment as concerns side-effects.

Secondary Aims include the assessment of neuro-inflammation and cognitive circuitry. We predict that TLT decreases plasma levels of IL6, IL8, TNF- $\alpha$ , IL-1 $\beta$  more than sham. TLT will also improve attention, inhibition and executive functions more than sham.

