B. Tolerability of the TLT: The frequency and severity of the reported side-effects and adverse events with the TLT will be compared in the TLT vs. Sham group (Fisher's Exact Test), following the SPCD design. The corrective measures adopted by the clinicians will also be reported, as well as the clinical judgment on the likelihood of the association of the side effect/ adverse event with the TLT.

C. Cognitive Tasks Analyses:

The secondary efficacy variable is the effect of TLT on cognitive performance as measured by selected cognitive tasks. All analyses will be conducted in accordance with SPCD design.

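### Section 4.9 limits the Adverse Events Form to TLT-related events, while Section 4.17 requires all events, so the TLT versus sham safety comparison could rest on events already screened for causality

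*Protocol*

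**What the plan says.** **The form.** Protocol Section 4.9 describes the Adverse Events Form as one that "captures any adverse event (serious or otherwise) specifically related to the application of the TLT". It adds that the form helps decide whether side effects are too great for a participant to continue.

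**The recording rule.** Section 4.17.1 states: "All adverse events will be recorded from the time of Informed Consent through study completion, or termination". Its definition of an adverse event needs no causal link to the device. Section 4.17.3 covers "all Adverse Events occurring during the study, whether or not attributed to the TPBM-1000 device or TLT procedure" and sends them to the subject's "source document and on the appropriate CRF pages". Relationship to the device or procedure is one of the attributes to be assigned to each event. The scale has five grades (None, Remote, Possible, Probable, Definite), and the lowest is defined as: "The Adverse Event is not associated with the study device use".

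**The hypothesis.** Section 5.2, Hypothesis 2, predicts that TLT will be safe and well tolerated, "as assessed by the following rating scales: SAFTEE-SI and ADVERSE EVENTS FORM". Section 4.9 says of the SAFTEE-SI that "it examines in a systematic fashion all possible treatment-emergent side effects and probes specific adverse symptoms".

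**The analysis.** Section 5.6 B states: "The frequency and severity of the reported side-effects and adverse events with the TLT will be compared in the TLT vs. Sham group", using Fisher's exact test. The clinicians' view of how likely an association is will be reported as well. Section 5.7 tabulates the number and percent of adverse events by group and type, with no restriction to related events. The SAP covers QIDS and HAM-D only.

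**The concern.** A randomised safety comparison normally counts every event in each arm and lets the difference between arms speak to causation. If events enter the dataset only after someone has judged them related, that judgement replaces part of what randomisation is there to provide. The events most easily lost are those nobody expects the device to cause, which is where a new device most needs the comparison.

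Safety and tolerability is the trial's second specific aim. Hypothesis 2 also anticipates a difference in side effects between TLT and sham, so the ability to detect such a difference matters. As the text stands, two analysts could build different safety tables from the same trial, one from related events and one from all events, and each could cite the protocol.

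**Working it through.** The plan states no figure on this point and no arithmetic bears on it. The check is a comparison of texts.

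1. **Can one form satisfy both rules?** No. Under 4.9 an event must be related to TLT to be entered. Under 4.17.1 and 4.17.3 every event is documented and then graded. A related-only form could never hold an event graded None, and would hardly hold one graded Remote. Section 4.9 does not say which of the five grades count as related.

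2. **Does the rest of the schedule fit 4.9?** Not well. Section 4.8.2.1 has the form completed at Visit 1 before the first treatment, when no TLT-related event can yet exist. Recording under 4.17.1 runs from consent, which is taken at screening, but the form first appears at Visit 1.

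3. **Is there another form for all events?** None is named. The Adverse Events Form is scheduled at Visit 1, at the 11 odd-numbered visits from 3 to 23, and at Visit 25: 1 + 11 + 1 = 13 visits, plus the exit visit on early withdrawal (4.8.2.1, 4.8.2.3, 4.8.3, 4.19.1). Attachment 1 lists no other adverse-event form. Section 4.17.1 mentions an Adverse Event CRF and 4.17.3 mentions CRF pages, but neither says whether these are separate from the form.

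4. **Do the analysis sections settle the source?** No. Section 5.6 B names no source, and its phrase about events with the TLT can mean either events during TLT or events due to it. Section 5.7 reads as all events but names no source either. The SAP is silent.

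5. **What follows if the form is the source and 4.9 is followed?** The counts in both arms would be limited to events judged related by clinicians who are to be blind (4.11). If a share *f* of device-caused events were judged unrelated, the excess visible on the form would be (1 − *f*) times the true excess. The documents give no value for *f*, no expected event rate and no share of background events, so *f* may lie anywhere from 0 to 1. No size can be stated.

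6. **What remains unfiltered?** The SAFTEE-SI is self-rated, has no stated causality filter, and is given at the same 13 visits. It would still show symptom differences between arms. The protocol does not say that it carries the attributes that 4.17.3 requires, such as onset, seriousness, relationship, action and outcome.

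**The case against.** The best defence is that the protocol's intent is plain and 4.9 is one loosely worded line. Section 4.17 defines and requires all events, the grade None makes sense only if unrelated events are kept, 5.6 B treats likelihood of association as something to report, and 5.7 counts adverse events without restriction. The form's stated role in decisions about continuing could also mean that it is a narrow tolerability record kept beside a full adverse-event CRF. Much of this stands: it shows that the remedy already matches the rest of the protocol. It does not remove the conflict, because that other CRF is not identified and the source for Fisher's test is left open.

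Three stronger readings are tempting, and the documents do not support them.

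- **That the safety comparison will be filtered.** No section makes this form the sole source for Fisher's test or for the 5.7 table, and Hypothesis 2 names the SAFTEE-SI as well.
- **That effects overlapping with depression would be left out.** Section 4.20.1 lists insomnia, irritability and word-finding difficulty as side effects documented in prior trials. Under 4.17.3, an event that follows device use in reasonable time but could come from the subject's clinical state is graded Possible. Overlap alone does not make it unrelated.
- **That the filter would bias one arm against the other.** Clinicians are to be blind, and Section 4.14 says that the visible and audible behaviour of the device is identical across modalities. A differential filter would need suspicion of assignment. Sections 3.2 and 4.2 say that active treatment cannot be felt as warming, while 4.20.1 allows for mild warmth, so this route cannot be excluded. Nothing in the documents shows that it would operate.

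**Conclusion.** The contradiction between 4.9 and Sections 4.17.1 and 4.17.3 is explicit and should be resolved. Its consequence for the analysis is conditional. If the Adverse Events Form is the data source, and if 4.9 is applied as written, the TLT versus sham comparison could be restricted to events judged related. With blinding intact, the main harm is reduced sensitivity, above all to effects not anticipated; the SAFTEE-SI offsets part of it. The size cannot be computed from the documents. This is an inconsistency in the text, with no sign that the investigators chose to filter events by causality.

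**What to change.** - **Section 4.9:** reconcile it with 4.17.3, so that the Adverse Events Form records every adverse event from consent onward, with the five-level relationship grade as a separate field. If a separate all-events CRF already exists, name it in 4.9 and 4.17.3 and add it to Attachment 1.
- **Sections 5.6 B and 5.7:** state that the TLT versus sham comparison uses all adverse events regardless of attribution, name the data source, and present related events as a subset with the grades that define it. A matching sentence in the SAP would close the gap there.

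The cost is a few sentences and slightly more data entry. No added visit is needed, and relationship is already a required attribute under 4.17.3.
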